3.4.1. Inclusion Criteria

Potential study subjects must meet the following inclusion criteria to be enrolled in this study.

1. Men and women \geq 18 years of age in sinus rhythm
2. Able to communicate effectively with trial personnel
3. LVEF measurements obtained via 2D Echo with or without contrast or other methods (e.g. CMR, MUGA scan) obtained within 6 months prior to enrollment (Day 0)
4. Has provided signed informed consent after receiving a verbal and written explanation of this clinical trial

3.4.2. Exclusion Criteria

Potential study subjects who meet any of the following criteria will be excluded from the study.

1. Female subjects who are pregnant or lactating. All women of child bearing potential [WOCBP] must have a negative urine pregnancy test at screening regardless of contraceptive use history.
2. Women of child-bearing potential are excluded unless they:
 - a. are post-menopausal defined as amenorrhea \geq 12 consecutive months, **OR**
 - b. have undergone successful surgical sterilization (hysterectomy, bilateral tubal ligation or bilateral oophorectomy), **OR**
 - c. have been using an adequate and medically approved method of contraception to avoid pregnancy for at least 1 month prior to DEFINITY® dose administration and be willing to continue using the same method for the duration of the study.
3. Current illness or pathology that would prevent undergoing investigational product administration due to a significant safety risk to the subject.
4. Uncontrolled arterial hypertension (defined as systolic blood pressure \geq 200 mmHg or diastolic blood pressure \geq 110 mmHg) or arterial hypotension (defined as systolic blood pressure \leq 90 mmHg).
5. Unstable cardiovascular status defined as:
 - a. myocardial infarction or unstable angina pectoris within 6 months prior to enrollment/DEFINITY® dose administration day
 - b. transient ischemic attack or stroke within 3 months prior to DEFINITY® dose administration
 - c. symptomatic valvular heart disease or moderate to severe stenotic valvular heart disease
 - d. clinically significant congenital heart defects
 - e. current uncontrolled cardiac arrhythmias causing symptoms or hemodynamic compromise
 - f. acute pulmonary embolus or pulmonary infarction
 - g. acute myocarditis or pericarditis
 - h. acute aortic dissection
 - i. atrial fibrillation
6. Any major surgery within 4 weeks prior to screening
7. Known contraindications to undergoing CMR (e.g. implanted pacemakers, cardioverter, defibrillators) or claustrophobia
8. Participation in any investigational drug, device, or placebo study within 30 days prior to screening
9. Known hypersensitivity to perflutren, or any of the excipients in DEFINITY®
10. Prisoners or those who are subject to compulsory detention or involuntary incarceration for treatment of either a psychiatric or physical illness (e.g., infectious disease)

3.5. Determination of Sample Size

The primary analysis is to demonstrate an improvement in LVEF accuracy from unenhanced imaging to imaging with DEFINITY® contrast enhancement using CMR as the truth standard.

This document is confidential.

For each subject, the absolute value of the difference of DEFINITY® LVEF minus CMR LVEF will be calculated. Similarly, the absolute value of the difference of unenhanced imaging LVEF minus CMR LVEF will be calculated for each subject. The primary analysis is to assess the significance of the difference between DEFINITY® and unenhanced echo with respect to the mean “absolute value of the difference versus CMR”. These means will be compared with a paired t-test at a two-sided 0.05 level of significance. Specifically, the null and alternative hypotheses are: H0: $\mu_D = \mu_U$ versus H1: $\mu_D \neq \mu_U$, where μ_D and μ_U are the mean of the DEFINITY® unenhanced echo absolute value of the difference versus CMRs, retrospectively. A sample size of 150 enrolled subjects has 90% power to reject the null hypothesis in favor of the alternative if the true difference $\mu_D - \mu_U$ is at least 2.75 (in favor of DEFINITY®) with a standard deviation of 10 or less and allows for approximately 5% premature withdrawal. Power was calculated using the PASS 15 software (NCSS,LLC).

3.6. Treatment Assignment & Blinding

There is only one treatment group in this open-label study.

To allow the statistical team to be able to work on the interim analysis (IA), without unblinding to the IA results, the statistical team will remain blinded to the reader and CMR reported results until all subjects complete the final study visit, or terminate early from the study, and the database has been locked. A separate unblinded statistical team will create the unblinded results to be reviewed during the IA.

3.7. Administration of Study Medication

DEFINITY® will be administered as a diluted bolus injection. 1.3 mL of activated DEFINITY® will be diluted with 8.7 mL of preservative-free saline to evenly distribute microspheres. An initial injection of up to 3 mL of diluted DEFINITY® will be administered with subsequent injections of 1 to 2 mL, as needed. Full details are available in the Dose Preparation and Administration Guide in the protocol.

3.8. Study Procedures and Flowchart

The schedule of events for this study is shown in Figure 1. A schedule of procedures is displayed in Appendix 13.1. Below is a description, by visit, of all activities.

3.8.1. Screening

All Screening/Baseline assessments will occur within 7 days prior to administration of study drug (Day 0).

- Determine eligibility according to inclusion/exclusion criteria
- Informed consent completed
- General medical history information collected
- Concomitant medications collected
- Physical examination conducted
- Vital signs collected
- Urine pregnancy test (as applicable)
- Adverse event collection

This document is confidential.

3.8.2. Echocardiography Imaging Session

Subjects providing informed consent and meeting the inclusion/not meeting the exclusion criteria will be enrolled into the study and undergo the following assessments on Day 0:

- Urine pregnancy test
- Concomitant medications collected
- Bedside resting transthoracic echocardiogram
- Following the unenhanced imaging scan, the study drug (DEFINITY®) will be administered
- Following study drug administration and subsequent image optimization, the same A2C, A3C, and A4C views will be obtained
- After completion of all assessments, subjects will remain on site for at least 30 minutes of observation
- Adverse event collection

3.8.3. Telephone Assessment

A safety follow-up call will be conducted for all subjects at approximately 72±24 hours after completion of the imaging sessions. Concomitant medications and adverse events will be collected during this call.

3.8.4. Cardiac Magnetic Resonance Imaging

Within ±30 days of the Day 0 imaging session, subjects will receive a non-contrast enhanced CMR examination as described in the Study Imaging Manual.

This document is confidential.

4. Endpoints

4.1. Primary Efficacy Endpoint

The primary endpoint of this study is improvement in accuracy in left ventricular ejection fraction (LVEF) assessment using DEFINITY® contrast-enhanced over unenhanced echocardiography. The primary analysis is to compare LVEF accuracy from unenhanced imaging to imaging with DEFINITY® contrast enhancement using cardiac magnetic resonance imaging (CMR) as the truth standard.

4.2. Secondary Efficacy Endpoints

The secondary endpoints are as follow:

- Improvement in accuracy in LVEF assessment using DEFINITY® contrast-enhanced over unenhanced echocardiography in subjects with suboptimal echocardiograms
- Reduction in inter-reader variability for the assessment of LVEF using DEFINITY® contrast-enhanced versus unenhanced echocardiography
- Reduction in inter-reader variability for the assessment of end-diastolic/systolic volumes using DEFINITY® contrast-enhanced versus unenhanced echocardiography
- Reduction in inter-reader variability for the assessment of LVEF using DEFINITY® contrast-enhanced versus unenhanced echocardiography in subjects with suboptimal echocardiograms
- Reduction in inter-reader variability for the assessment of end-diastolic/systolic volumes using DEFINITY® contrast-enhanced versus unenhanced echocardiography in subjects with suboptimal echocardiograms

4.3. Safety Endpoints

Enrolled subjects will be followed for AEs, SAEs, and changes in concomitant medications from the time the informed consent is signed through 72±24 hours after completion of DEFINITY® administration.

This document is confidential.

5. Analysis Sets

There will be 5 populations for this study. They are listed below.

5.1. Screened Population

The Screened Set will include all subjects screened in the study. Unless specified otherwise, this set will be used for subject listings and summaries of subject disposition.

5.2. Safety Population

The Safety population (SP) will include all subjects who have signed an informed consent and who have received any amount of DEFINITY® in the study. This is the primary analysis population for the safety analysis. Unless otherwise stated, the SP will be used for all analyses of safety endpoints and for the presentation of subjects in all subject listings.

5.3. Intent-to-Treat Population

The Intent-to-Treat (ITT) population will include all subjects who have signed an informed consent.

5.4. Modified Intent-to-Treat Population

The Modified Intent-to-Treat (mITT) population will include all ITT subjects who complete unenhanced imaging, DEFINITY®-enhanced imaging, and cardiac MRI assessments. This is the primary analysis population for the efficacy endpoints.

5.5. Per-Protocol Population

The Per-Protocol (PP) population will include all subjects in the mITT population who

- a) Did not violate inclusion and/or exclusion criteria that would likely have an effect on the primary outcome;
- b) Do not have major protocol violations;
- c) Have LVEF data on both unenhanced and DEFINITY®-enhanced for at least one reader; and
- d) Have CMR LVEF.

Efficacy analyses will be conducted for both the mITT and PP populations. Differences in results between the 2 populations will be carefully examined.

5.6. Protocol Deviations

Deviations from the protocol, as defined in the protocol, will be documented and monitored on an ongoing basis by the Sponsor, study monitors, and project manager throughout the study.

Prior to database lock, the study team will forward all relevant protocol violation documentation in a pre-specified format to the study statistician. These violations will be used to determine eligibility for the PP population and will be listed in a separate report to be included in the clinical study report.

This document is confidential.

6. General Aspects for Statistical Analysis

6.1. General Methods

Syneos Health will be responsible for data management and statistical analysis. All statistical analyses will be performed using SAS version 9.4 or higher. Subject data listings and tabular presentations will be provided. Summary statistics for continuous variables will include, unless otherwise stated, the following values: N, mean, median, standard deviation, minimum, and maximum. For categorical variables, the number and percent of subjects in each category will be calculated, while the number of subjects with missing data will be presented as a 'Missing' category. Unless otherwise stated, subjects with missing values will be included in the denominator count when computing percentages.

Results will be presented to 1 decimal place when applicable. All statistical tests will be two-sided employing a significance level of 5% unless otherwise specified. Further details of each analysis will be described in the appropriate section.

Demographic and efficacy analyses will be conducted on the mITT population as the main analysis population. Efficacy analyses will also be conducted on the PP population. The safety analyses will be conducted on the SP.

The primary analysis will be performed on subjects with non-missing LVEF for DEFINITY®-enhanced echocardiography imaging, unenhanced imaging, and the truth standard CMR. A supportive analysis will be conducted where missing LVEF is multiply imputed using the fully conditional specification (FCS) multiple regression, as detailed in section 6.2. Otherwise, there will be no imputation of missing efficacy data.

6.2. Missing Data

There will be no imputations for missing efficacy data except the supportive primary endpoint paired t-test. For all other analyses, the number of subjects with missing data will be presented under a 'Missing' category. Unless otherwise stated, subjects with missing values will be included in the denominator count when computing percentages. When continuous data are being summarized, only the non-missing values will be evaluated for computing summary statistics.

6.2.1. Primary Supportive Analysis

A supportive analysis will be run where, within each blinded reader, missing LVEF is multiply imputed using the FCS multiple regression prior to carrying out the primary endpoint analysis. The covariates in the imputation model will be study center, age, gender, body weight (kg), race, and ethnicity. This procedure will be done separately for each imaging method (DEFINITY® enhanced, unenhanced, and CMR truth standard). A total of 50 imputations will be generated. The paired t-test comparing mean bias between DEFINITY® and unenhanced (see primary endpoint null and alternative hypotheses in section 3.5) will be performed separately on each of the 50 imputed datasets, and the t-test results will be combined across datasets using the usual multiple imputation techniques to create one overall paired t-test results on imputed data.

This document is confidential.

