Assessment Across Study Centers: The mean “absolute value of the difference vs. CMR” for each DEFINITY® and unenhanced echocardiography, as well as the difference between the two treatments with respect to this mean, will be presented for each study center and blinded reader. Within each blinded reader, an assessment of study center effect on the mean treatment difference will be carried out using one-way analysis of variance. For each blinded reader, a site difference that is not significant at the 0.15 level of significance, or a site difference that is significant but where for every site the mean treatment difference is more favorable for DEFINITY® than enhanced echocardiography, will support pooling subjects across sites for the primary analysis for that reader.

Missing Data: Within each blinded reader, the primary analysis will be performed on subjects with non-missing LVEF for DEFINITY®, unenhanced echocardiography, and the reference standard. A supportive analysis will be run where, within each blinded reader, missing LVEF is multiply imputed using the fully conditional specification (FCS) multiple regression. The covariates in the imputation model will be fully specified in the formal

statistical analysis plan and will include baseline and demographic variables and will also include imaging method (DEFINITY®, unenhanced, or CMR reference standard). A total of 50 imputations will be generated; the paired t-test comparing mean bias between DEFINITY® and unenhanced will be performed separately on each of the 50 imputed datasets, and the t-test results will be combined across datasets using the usual multiple imputation techniques to create one overall paired t-test results on imputed data.

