3.3. Brief Description

This is a Phase 3, prospective, open-label, multicenter study to evaluate LVEF measurement accuracy and reproducibility of DEFINITY® contrast-enhanced and unenhanced echocardiography as compared with non-contrast cardiac magnetic resonance imaging (CMR) used as the truth standard. Approximately one-hundred fifty (150) subjects will be enrolled over approximately 10 months at approximately 10 centers located in the United States. The study population will consist of male and female subjects 18 years of age of older.

Subjects will be screened based on LVEF measurements obtained via 2D echo with or without contrast or other methods (e.g. CMR, MUGA scan) obtained within 6 months of enrollment (Day 0). Subjects will be stratified to achieve an approximately even distribution within four pre-defined LVEF groups (>50, 41-50, 30-40, <30%). LVEF for screening purposes will be determined by the investigator and based on measurements with 2D echo or other methods (e.g. CMR, MUGA scan) obtained within 6 months prior to enrollment (Day 0). The site investigator will determine whether an echocardiogram is optimal or sub-optimal based on the unenhanced echocardiogram performed on Day 0. Subjects with optimal and sub-optimal echocardiograms (based on investigator opinion) will be enrolled. An echocardiogram is considered sub-optimal if 2 or more segments of the ventricular border are classified as not adequately visualized.

Each subject will undergo an unenhanced ultrasound examination and a DEFINITY® contrast-enhanced examination on the same day at Day 0. A minimum of 360 seconds of images will be collected during both the unenhanced and the DEFINITY® contrast-enhanced examinations. Subjects will remain at the clinical site for at least 30 minutes of observation after DEFINITY® administration. A safety follow-up

This document is confidential.

phone call will be conducted for all subjects at approximately 72 ± 24 hours after completion of the imaging sessions, including DEFINITY® administration.

Enrolled subjects will be followed for adverse events (AEs), serious adverse events (SAEs), and changes in concomitant medications from the time the Informed Consent is signed through the safety follow-up telephone call.

A non-contrast CMR will be used as the truth standard. CMR studies will be performed within ±30 days of the echocardiographic assessments at Day 0. Final assignment of each subject to an LVEF group will be determined by CMR.

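### SAP 6.2.1 imputes missing LVEF from study center and demographics alone, so the only missing-data analysis is biased against whichever echo modality has more missing reads

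*SAP*

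**What the plan says.** SAP 6.2 limits imputation of efficacy data to a single analysis: "There will be no imputations for missing efficacy data except the supportive primary endpoint paired t-test". SAP 6.2.1 describes it: "within each blinded reader, missing LVEF is multiply imputed using the FCS multiple regression prior to carrying out the primary endpoint analysis". The predictors are then listed: "The covariates in the imputation model will be study center, age, gender, body weight (kg), race, and ethnicity". The next sentence adds: "This procedure will be done separately for each imaging method", naming enhanced echo, unenhanced echo and CMR. Fifty imputations are generated, a paired t-test is run on each, and the results are pooled.

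Protocol 8.2.1 (Missing Data) left the covariates to the SAP. It said that they would comprise baseline and demographic variables together with imaging method. SAP 11.1 reports no change from the protocol.

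The primary analysis (SAP 8.1) uses mITT subjects with all three LVEF values present. SAP 5.4 defines mITT as "all ITT subjects who complete unenhanced imaging, DEFINITY®-enhanced imaging, and cardiac MRI assessments".

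**The concern.** The endpoint is |echo LVEF − CMR LVEF| in the same subject. A model that imputes one half of that difference has to know the other half. Under SAP 6.2.1 it does not: the covariate list contains no LVEF, and each method is imputed in its own run. The subject's CMR LVEF, other echo LVEF and screening LVEF all play no part.

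A missing echo value is therefore drawn from roughly the whole distribution of LVEF in the trial. Enrollment deliberately widens that distribution, aiming for an "approximately even distribution within four pre-defined LVEF groups (>50, 41-50, 30-40, <30"%). The imputed absolute error is then far too large, and the modality with more missing reads is penalized. This happens even when reads are missing completely at random, a case in which the complete-case analysis is unbiased.

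At stake is the only check on missing LVEF. The per-protocol, RMSE, Bland-Altman, Deming and ICC analyses do not address it. The check could contradict a sound primary result, or appear to strengthen it, merely because reads are missing unevenly.

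**Working it through.** **The plan's own figure.** SAP 3.5 claims 90% power with 150 enrolled if the true difference "is at least 2.75 (in favor of DEFINITY®) with a standard deviation of 10 or less". With 143 evaluable subjects (SAP 10), the noncentrality is 2.75/10 × √143 = 3.29 and the critical value is 1.97681. Power is 90.4%, so the figure reproduces.

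**Inputs.** From the documents: n = 143, two-sided 0.05 paired t-test, 50 imputations, planning SD 10. Assumed, because the documents do not give them: LVEF SD 13, CMR error SD 3, covariate R² 0.10, reads missing at random, and all missing rates. Under the null, echo error SD is 11.3 for both methods. This gives a paired SD of about 9.9, matching the planning SD.

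**Closed form, null case.**

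- True mean absolute error: √(2/π) × √(11.3² + 3²) = 0.798 × 11.69 = 9.3.
- Imputed as in SAP 6.2.1: √(2/π) × √[(13² + 11.3²) + (13² + 3²) − 2 × 0.10 × 13²] = 0.798 × √440.9 = 16.8.
- Gap 7.4 points (before rounding). Expected drift is the missing rate × 7.4: 0.37 at 5% and 0.74 at 10%.

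**Closed form, planned alternative.** Unenhanced error SD is 12.9 and enhanced 9.3.

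- True difference: 0.798 × (13.24 − 9.77) = 2.77.
- Imputed enhanced error: 0.798 × √400.7 = 15.97, against a true 7.80. The gap is 8.17.
- With only enhanced reads missing: 2.77 − 0.05 × 8.17 = 2.36, and 2.77 − 0.10 × 8.17 = 1.95.

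**Simulation.** Bayesian regression imputation, 50 imputations, Rubin's rules with small-sample degrees of freedom. There were 4,000 null trials per one-sided missingness scenario, 1,000 per two-sided scenario, and 3,000 per alternative scenario. All rates are per reader. The joint model lets the three LVEF values predict one another.

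| Scenario | SAP 6.2.1 | Complete case | Joint model |
|---|---|---|---|
| Null, unenhanced 2% missing | +0.15; 3.1% toward DEFINITY | – | – |
| Null, unenhanced 5% | +0.38; 5.5% | 2.8% | +0.02; 2.9% |
| Null, unenhanced 10% | +0.76; 9.5% | 2.4% | +0.03; 2.8% |
| Null, enhanced 5% / 10% | −0.38 / −0.76; 4.9% / 8.2% against DEFINITY | – | – |
| Null, 5% in each | 0.00 | – | – |
| Null, unenhanced 5%, enhanced 3% | +0.14; 2.9% | – | – |
| Alternative, enhanced 5% | estimate 2.36; power 76% | power 90% | power 91% |
| Alternative, enhanced 10% | estimate 1.95; power 53% | power 90% | power 92% |

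The nominal one-sided rate is 2.5%. With 1,000 trials its simulation error is √(0.025 × 0.975/1000) = 0.5%, so the 2.9% in the 5%/3% row cannot be told apart from nominal.

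**Sensitivity, null, unenhanced-only missing at 5% / 10%.**

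- LVEF SD 12 to 16: drift 0.33–0.51 / 0.65–1.02.
- Echo error SD 8 (paired SD 7.2): false rejection 7.7% / 16.5%.
- A less favorable set (even strata spanning 15–70%, giving LVEF SD about 14.5; echo error SD 8 with correlated echo errors; no CMR error; 250 trials, 20 imputations): drift +0.58 / +1.14, false rejection 11% / 26%. With CMR and the other echo in the model, the 10% case returns to +0.08 and 2.4%.

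**The case against.** The strongest reply is that the size is unknown and may be small. No missing-read rate is given. The only attrition figure, 5% premature withdrawal, falls largely outside mITT, because mITT requires all three studies to be completed. SAP 6.2.1 does not name its population, but SAP 6.1 makes mITT the main efficacy set. Protocol 6.8.2 has a technologist supply initial contours, which may limit missing reads further. This stands: at 2% missing, or at 5% against 3%, the false-rejection rate barely moves.

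The simulations also assume missingness unrelated to error, whereas unreadable images plausibly carry larger errors. If missing unenhanced reads had 1.5 times the error SD, their true mean absolute error would be 0.798 × √(16.95² + 3²) = 13.7. The gap shrinks to 3.0 and the 5% drift to 0.15. At 2 times, the drift is −0.07. This stands as a limit on the magnitude. Any such cancellation would be accidental, and complete case would no longer be unbiased either.

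Balanced missingness is not free. Under the planned alternative with 5% missing in each echo modality, the estimate is 2.70 against 2.75 for complete case, but power is 83% against 90%. Missing CMR pulls the difference toward zero: with 10% missing, 2.68 against 2.81 for complete case. Both add to the point.

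Finally, FCS is a chained method with little purpose when one variable is incomplete, and the protocol named imaging method as part of the model. One could infer that a joint model was intended. The SAP's instruction to impute each method separately rules that out as written, and an imaging-method covariate would not by itself link a subject's echo to that subject's CMR. The mismatch with SAP 11.1 should be reconciled.

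**Conclusion.** The concern holds. Followed as written, SAP 6.2.1 imputes absolute errors that are far too large, and the result moves against the echo modality with more missing reads. Under the base assumptions the drift is about 0.074 points for each 1% of reads missing in one modality only under the null, against a design effect of 2.75.

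Confidence is high on the defect and its direction when reads are missing at random. The size depends on assumed missing rates and variances. It is small when missingness is rare or balanced, and it could shrink or reverse if unreadable images have much larger errors. The rates above are per reader, not for the two-of-three success rule, and no success rule attaches to this supportive analysis. The primary complete-case decision and the 90% power claim are unaffected. The section should be corrected because it is the only analysis that addresses missing LVEF.

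**What to change.** In SAP 6.2.1, replace the separate imputations with one FCS model per reader on one row per subject. Enhanced, unenhanced and CMR LVEF should be mutual predictors, with the listed covariates retained. Screening LVEF, which every subject must have for entry, could be added if it is in the database. Compute the absolute differences after imputation, then run and pool the paired t-tests.

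Name the analysis population, report missing LVEF counts by modality and reader beside the result, and record in SAP 11.1 how the model relates to Protocol 8.2.1.

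As a wording correction only, align the test description. Protocol 8.2.1 says "the paired t-test comparing mean bias between DEFINITY® and unenhanced will be performed separately", and SAP 6.2.1 uses the same term, while the hypotheses in SAP 3.5 concern the mean absolute difference versus CMR.

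The cost is SAP text and a few lines of code on data already collected. A small residual drift can remain at higher missing rates, and the model still assumes missing at random.

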8.1. Primary Efficacy Endpoint and Analysis

The primary endpoint is LVEF accuracy. The primary analysis is to demonstrate an improvement in LVEF accuracy from unenhanced imaging to that derived from imaging with DEFINITY® contrast enhancement using CMR as the truth standard.

For each subject, the absolute value of the difference of DEFINITY® LVEF minus CMR LVEF will be calculated. Similarly, the absolute value of the difference of unenhanced imaging LVEF minus CMR LVEF will be calculated for each subject. The primary analysis is to assess the significance of the difference between DEFINITY® and unenhanced echo with respect to the mean “absolute value of the difference versus CMR”.

The null and alternative hypotheses for this study are:

$$H_0: \mu_D = \mu_U \text{ versus } H_1: \mu_D \neq \mu_U; \text{ or, that is}$$

$$H_0: \mu_U - \mu_D = 0 \text{ versus } H_1: \mu_U - \mu_D \neq 0$$

where μ_D and the μ_U are the mean of the DEFINITY® and unenhanced echo absolute value of the difference versus CMR, retrospectively. The null hypothesis will be tested at a two-sided 0.05 level of significance using a paired t-test derived from the sample point estimates of the mean and standard deviation of the difference between unenhanced echo's and DEFINITY's® “absolute value of the difference versus CMR”.

The analyses will be conducted separately for each of the three blinded readers of the DEFINITY® enhanced and unenhanced images. The criterion for success is that the null hypothesis is rejected in favor of DEFINITY® for at least 2 of 3 blinded readers for all subjects. CMR LVEF will be used as the comparator for each of the 3 blinded readers, and is interpreted by a single reader.

The primary analysis will be performed on mITT subjects with non-missing LVEF for DEFINITY®, unenhanced echocardiography, and the truth standard. A supportive analysis will be run where a missing echocardiography or CMR LVEF is multiply imputed using the fully conditional specification (FCS) multiple regression as described in section 6.2.1.

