8.1.1. Other Analyses for the Primary Endpoint

The following will be carried out separately for each of the 3 blinded readers without imputation of missing LVEF.

Bias is the mean of the actual (not absolute value) per-subject differences between the imaged LVEF and CMR LVEF. The bias, the two-sided 95% confidence interval (CI) of the bias, the precision (standard deviation of the per-subject differences) and the root mean square error (RMSE) will be calculated for the LVEF derived from the DEFINITY®-enhanced images. The RMSE is the square root of the bias-squared + precision-squared and is considered a measure of overall accuracy. These analyses will be repeated for

This document is confidential.

LVEF values derived from the unenhanced echocardiography versus those from CMR. It is anticipated that the RMSE will be smaller for DEFINITY®-enhanced LVEF than for unenhanced LVEF.

DEFINITY®-enhanced and unenhanced echocardiography LVEF will each be assessed for measurement accuracy against the reference CMR using Bland-Altman analysis and Deming regression analysis. For the Bland-Altman analysis, a plot of the per-subject actual difference between DEFINITY®-enhanced echocardiography and CMR LVEF will be plotted versus the per-subject sum of the two measurements. Limits of agreement (defined as the mean of the DEFINITY® versus CMR difference) ± 2 standard deviations will be shown on the plot. The same analyses will be performed for unenhanced echocardiography using CMR as the reference standard.

Deming regression plots of LVEF versus CMR LVEF will be generated for each of DEFINITY®-enhanced and unenhanced echocardiography. Unweighted Deming regression will be employed to estimate the regression slope and intercept with two-sided 95% CI of each assuming the measurement error is the same for CMR and each of the echocardiography error techniques.

The intra-class correlation coefficient (ICC) and its two-sided 95% CI will be calculated for DEFINITY®-enhanced echo versus CMR and for unenhanced echo versus CMR. The ICCs and their two-sided CIs will be calculated using between and within mean squares from an ANOVA model with method (echocardiography, CMR) and subject as the main effects and LVEF as the dependent variable. The ICC will be calculated using the SAS macro developed by Hamer (1990).

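### The imputed-data supportive test is worded as a comparison of mean bias, a signed quantity in both documents, although the absolute-error primary test is evidently meant; the wording should be aligned

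*SAP*

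**What the plan says.** **Primary endpoint.** SAP 3.5 builds the primary test on the unsigned gap between echo and CMR: "The primary analysis is to assess the significance of the difference between DEFINITY® and unenhanced echo with respect to the mean “absolute value of the" (the quote stops just before CMR is named as comparator). On the method, that section says: "These means will be compared with a paired t-test at a two-sided 0.05 level of significance". SAP 8.1 and Protocol 8.2.1 define the same test. It is run for each blinded reader on mITT subjects with all three LVEF values present.

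**Definition of bias.** SAP 8.1.1: "Bias is the mean of the actual (not absolute value) per-subject differences between the imaged LVEF and CMR LVEF". Protocol 8.2.1 gives the same definition.

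**Supportive analysis, SAP.** Section 6.2.1 says that, within each reader, "missing LVEF is multiply imputed using the FCS multiple regression prior to carrying out the primary endpoint analysis". It then specifies the test to be run on each imputed dataset: "The paired t-test comparing mean bias between DEFINITY® and unenhanced (see primary endpoint null and alternative hypotheses in section 3.5"). Section 6.2 makes this the only imputation of efficacy data: "There will be no imputations for missing efficacy data except the supportive primary endpoint paired t-test".

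**Supportive analysis, Protocol.** The Missing Data paragraph of 8.2.1 says: "the paired t-test comparing mean bias between DEFINITY® and unenhanced will be performed separately on each of the 50 imputed datasets". That paragraph does not refer to the hypotheses.

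**The concern.** The plan gives bias a fixed meaning, and the parenthesis in the definition separates it from the absolute-value metric of the primary endpoint. The imputed-data test is then specified with that defined term. A programmer who follows the definition would analyse signed differences, a variable that must be derived anyway for the bias, precision and RMSE tables in SAP 8.1.1. The slip would be easy to make and hard to notice.

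This is the only planned analysis that shows whether the complete-case primary result survives missing LVEF values. The per-protocol analysis does not do so: that population requires a CMR LVEF and paired echo LVEFs from at least one reader. If the wording stays open, two tests that can give opposite answers could both be defended from the text once results are known.

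**Working it through.** **1. The plan's own figure.** Inputs from SAP 3.5 and 10: difference 2.75, SD 10, two-sided 0.05, 150 enrolled, about 143 evaluable. The noncentrality parameter is 2.75/10 × √143 = 3.289 and the critical t on 142 df is 1.97681, as the SAP states. Noncentral-t power is 90.4%, against 90% stated. For 90% power 141 evaluable subjects are needed, and 141/0.95 gives 149 enrolled, against 150 stated. The design figures reproduce, and they belong to the absolute-error test.

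**2. The literal test.** Let D, U and C be one subject's DEFINITY, unenhanced and CMR LVEF.

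- Primary test variable: |U − C| − |D − C|
- Signed-bias test variable: (D − C) − (U − C) = D − U

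C drops out of the second. The test then asks whether the two echo methods differ on average, not which is closer to CMR. For a subject missing only CMR, the imputed CMR value would have no influence on that subject's contribution, although SAP 8.1 provides for imputing CMR LVEF.

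**3. Can the two tests disagree?** The documents give no biases, SDs or error correlation, so everything here is assumed: normal signed errors, 143 complete subjects, correlation 0.3, 20,000 replicates. For an error with mean m and SD s, the mean absolute error is s√(2/π)·exp(−m²/2s²) + m[1 − 2Φ(−m/s)].

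| Assumed errors (DEFINITY; unenhanced) | Gain in mean absolute error | Absolute-error test rejects | Signed test rejects |
|---|---|---|---|
| bias 0, SD 8; bias 0, SD 11.5 | 9.18 − 6.38 = 2.79 | 98.7% | 5.1% |
| bias +5, SD 9; bias −5, SD 9 | 8.26 − 8.26 = 0 | 5.1% | 100% |
| bias 0, SD 9; bias −6, SD 9 | 8.72 − 7.18 = 1.54 | 61% | 100% |
| bias 0, SD 8; bias −2, SD 11.3 | 9.16 − 6.38 = 2.77 | 98.4% | 52.5% |

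Rejection is in either direction in both columns. I repeated the runs with correlations of 0, 0.3, 0.4 and 0.7 (10,000 replicates each). Row 1 gave 98% to over 99.9% against about 5%. Row 2 gave about 5% against 100%. Row 3 gave 60–74% against about 100%, and row 4 gave 98% to over 99.9% against 40–84%. The disagreement does not depend on the correlation chosen.

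These runs contain no missing data and no imputation. They show that the two test variables are not interchangeable; they do not predict the result of the supportive analysis.

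**4. Which test do the documents mean?**

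| Place | Points to |
|---|---|
| SAP 6.2.1, the term mean bias | signed |
| SAP 6.2.1, same sentence, pointer to 3.5 | absolute |
| SAP 6.2.1, imputation precedes the primary endpoint analysis | absolute |
| SAP 6.2, names it the primary endpoint t-test | absolute |
| SAP 8.1, attaches it to the primary test | absolute |
| SAP 8.1.1, bias analyses run without imputation | absolute |
| Protocol 8.2.1, Missing Data, the term mean bias | signed |
| Protocol 8.2.1, place within the primary endpoint section | absolute, by implication |

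**The case against.** A reader might infer that the supportive analysis tests the wrong endpoint. The documents do not support that. The SAP sentence refers to the hypotheses in section 3.5, where both means are of absolute differences. SAP 6.2 and 6.2.1 say that the primary endpoint test is what is run on the imputed data. SAP 8.1.1 says its analyses, signed bias among them, are done without imputation, so an imputed signed-bias test would break both that rule and the one in 6.2. Neither document plans a paired t-test on signed bias elsewhere; bias is reported for each method with its own confidence interval. In the Protocol, the only paired t-test already defined in 8.2.1 is the absolute-error one, and that section leaves further detail of the imputation to the SAP.

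It is also fair to object that the simulated contrasts concern a test the sponsor probably does not intend, under inputs of my choosing.

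Both objections stand, and they make this a point about wording. They do not remove it: the operative sentence in each document still names a defined quantity that is not the primary endpoint, the Protocol paragraph carries no pointer to correct it, and neither document says that the absolute differences are to be recomputed from the imputed LVEFs.

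**Conclusion.** The point holds as an inconsistency of wording in an operative analysis rule. SAP 6.2.1 contradicts itself on the test variable. The Missing Data paragraph of Protocol 8.2.1 is literally wrong, although its position implies the absolute-error test. That the literal test drops CMR is algebra and needs no assumption; the size of any disagreement with the primary test does rest on assumed biases, SDs and correlations, and is illustrative only.

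Severity is low to moderate. The supportive analysis has no part in the success criterion, which rests on the complete-case test in at least two of three readers. Sample size, the stated 90% power and the primary analysis do not change.

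**What to change.** In SAP 6.2.1 and in the Missing Data paragraph of Protocol 8.2.1, replace *comparing mean bias* with *comparing the mean absolute value of the difference versus CMR*. Add that |echo LVEF − CMR LVEF| is recomputed for each method from the completed LVEF values in each of the 50 imputed datasets, before the paired t-test is run and the results are combined. Keep the SAP's pointer to section 3.5 and put the same reference to the primary hypotheses in the Protocol paragraph.

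The cost is a sentence or two in each document. No analysis is added and no design figure changes. The correction should be made before the results are unblinded.
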